#### **SECONDARY ENDPOINTS**

- 1) Percentage of ICOS+ CD4 T cells will be determined by CyTOF in blood, tumor, and bone marrow
- 2) PD-L1 expression will be determined in tumor tissue by IHC (Ventana assay); PD-L1 will also be determined on immune cell subsets by CyTOF in blood, tumor, and bone marrow.
- 3) NanoString gene expression arrays will be used to compare the gene expression of 300 immune-related genes in frozen tumor tissue obtained preoperatively and postoperatively.
- 4) Overall and recurrence-free survival survival will be measured according to our usual routine follow-up protocol and compared with historical controls. These analysis will be post-protocol analysis based upon data obtained from the standard of care follow up in our post-surgical patients.
- 5) A comprehensive evaluation of immune cell composition and phenotype will performed in preoperative and postoperative tumor tissue and peripheral blood, as well as bone marrow. **Appendix C** outlines the complete CyTOF panel that will be used for each individual specimen. Substudies will include:
  - a. Changes in T-cell subset (i.e., CD4, CD8, FoxP3) frequency and memory and activation phenotype (i.e., CD25, CD127, CD45RA, CD62L, CCR4, CCR6, Tim1).
  - b. Changes in the T-cell polarization state (intracellular interferon-gamma, TNF-alpha, IL-17, IL-2).
  - c. Changes in myeloid cell composition: dendritic cell, macrophage, MDSC, neutrophil (i.e., HLA-DR, CD11c, BDCA-1, BDCA-2, BDCA-3, BDCA-4, CD68, CD163, CD206, CD66b, CD15).
  - d. Changes in NK cell and NK T-cell composition (i.e., CD56, CD3, V224, Vbeta1)

For all experiments requiring tissue, whereas relatively large tissue samples are generally obtainable from both pre-resection biopsies performed by thoracoscopy, and at the time of tumor resection, our experiments will be prioritized as follows:

- 1) CyTOF
- 2) IHC
- 3) Gene expression

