### **2.2 Secondary objective(s)**

The secondary objectives of this study are:

- 1) Comparison of the percentage of inducible T-cell co-stimulator (ICOS) positive intratumoral CD4 T cells before and after treatment with combination MEDI-4736 and Tremelimumab checkpoint inhibitor therapy.
- 2) Comparison of tumor tissue expression (Ventana assay) of programmed death-ligand 1 (PD-L1) before and after treatment with combination MEDI-4736 and Tremelimumab checkpoint inhibitor therapy.
- 3) Comparison of the ratio of the intratumoral CD8/Treg ratio in patients treated with combination therapy (MEDI-4736 and Tremelimumab) compared to either patients treated with MEDI-4736 alone, and separately compare to untreated patients.
- 4) Comparison of the percentage of inducible T-cell co-stimulator (ICOS) positive intratumoral CD4 T cells in patients treated with combination therapy (MEDI-4736 and Tremelimumab) compared to either patients treated with MEDI-4736 alone, and separately compare to untreated patients.

- 5) Comparison of tumor tissue expression (Ventana assay) of programmed death-ligand 1 (PD-L1) in patients treated with combination therapy (MEDI-4736 and Tremelimumab) compared to either patients treated with MEDI-4736 alone, and separately compare to untreated patients. These analysis will be post-protocol analysis based upon data obtained from the standard of care follow up in our post-surgical patients.
- 6) Comparison of overall survival in patients treated with either MEDI-4736 alone or MEDI-4736 plus Tremelimumab with historical untreated controls. These analysis will be post-protocol analysis based upon data obtained from the standard of care follow up in our post-surgical patients.
- 7) Comparison of recurrence-free survival in patients treated with either MEDI-4736 alone or MEDI-4736 plus Tremelimumab with historical untreated controls. These analysis will be post-protocol analysis based upon data obtained from the standard of care follow up in our post-surgical patients.

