Tumor tissues obtained either by thorascopic biopsy or by resectional surgery will be evaluated by time-of-flight mass spectrometry (CyTOF) to determine intratumoral CD8/Treg ratios and percentage of ICOS positive CD4 T cells, and by immunohistochemistry (Ventana assay) to determine the tissue expression of PD-L1. These variables will be compared before and after treatment (changes within the same patient tumor), or between treatment groups (MEDI-4736 alone, MEDI-4736+tremelimumab, untreated) following treatment. Additional hypothesis-generating analyses will include a comprehensive systems based evaluation of the intratumoral immune cell population composition and phenotype phenotype [e.g., dendritic cells, macrophages, myeloid derived suppressor cells (MDSC), neutrophils, T-cell subsets, natural killer (NK) cells, and B cells], and immune-related gene expression using the nanostring system within the tumors, blood, and bone marrow of patients in all treatment groups.

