## **TREATMENT PLAN**

### **5.3 Subject enrollment and randomization**

We expect to enroll a total of 20 evaluable subjects (if tissue obtained at time of thoracoscopy and time of surgical resection) with surgically resectable MPM to this study over a period of 24 months. Subjects will be randomized. Subjects will be assigned to one of the three treatments (n = 8 MEDI4736, n = 8 MEDI4736 + tremelimumab, and n=4 control). All subjects will undergo surgical resection one to six weeks after the infusion.

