### **8.1.2 Secondary Efficacy Variables**

The secondary objectives of this study are:

- 1) Comparison of the percentage of inducible T-cell co-stimulator (ICOS) positive intratumoral CD4 T cells before and after treatment with combination MEDI-4736 and Tremelimumab checkpoint inhibitor therapy. These data will be obtained using CyTOF
- 2) Comparison of tumor tissue expression (Ventana assay) of programmed death-ligand 1 (PD-L1) before and after treatment with combination MEDI-4736 and Tremelimumab checkpoint inhibitor therapy. These data will be obtained with IHC.
- 3) Comparison of the ratio of the intratumoral CD8/Treg ratio in patients treated with combination therapy (MEDI-4736 and Tremelimumab) compared to either patients treated with MEDI-4736 alone, and separately compare to untreated patients. These data will be obtained with CyTOF.
- 4) Comparison of the percentage of inducible T-cell co-stimulator (ICOS) positive intratumoral CD4 T cells in patients treated with combination therapy (MEDI-4736 and Tremelimumab) compared to either patients treated with MEDI-4736 alone, and separately compare to untreated patients. These data will be obtained with CyTOF.
- 5) Comparison of tumor tissue expression (Ventana assay) of programmed death-ligand 1 (PD-L1) in patients treated with combination therapy (MEDI-4736 and Tremelimumab) compared to either patients treated with MEDI-4736 alone, and separately compare to untreated patients. These data will be obtained with IHC.
- 6) Comparison of overall survival in patients treated with either MEDI-4736 alone or MEDI-4736 plus Tremelimumab with historical untreated controls. These data will be obtained from our standard of care follow up of these patients. Given the survival estimates of these patients from historical controls, these data can be evaluated approximately 2 year after surgery. These analysis will be post-protocol analysis based upon data obtained from the standard of care follow up in our post-surgical patients.

7) Comparison of recurrence-free survival in patients treated with either MEDI-4736 alone or MEDI-4736 plus Tremelimumab with historical untreated controls. Given the recurrence free survival estimates of these patients from historical controls, these data can be evaluated approximately 2 year after surgery. These analysis will be post-protocol analysis based upon data obtained from the standard of care follow up in our post-surgical patients.

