### **10.3 Analysis plan**

There will be two treatment arms (MEDI4736 only and combination MEDI4736+tremelimumab) and one untreated arm (control). Randomization, stratified by receiving previous chemotherapy or not, will help to minimize patient selection biases between three arms. Preliminary tests will be performed to assess whether our data is normally or non-normally distributed. Patient characteristics will be summarized descriptively. Baseline characteristics will be compared by treatment assignment. For our primary objective that compares outcome variable in tissues before and after treatment with combination MEDI4736

Clinical Study Protocol

Drug Substance Tremelimumab

Study Number **ESR-14-10744**

Edition Number 8

Date 17 April 2019

and tremelimumab, we will use a paired t-test in log-transformed ratio of intratumoral cytotoxic T cells to regulatory T cells (CD8/Treg) before and after the treatment. In our secondary objective numerous variable comparisons are made between tumor tissues from untreated patients with from patients undergoing treatment with either MEDI4736 or MEDI4736 + tremelimumab, and between tumor tissues from patients undergoing treatment with MEDI4736 and tumor tissues from patients undergoing treatment with MEDI4736+tremelimumab. In these comparisons, a paired t-test or Student t-tests will be performed. Because approximately 20 comparisons of immune cell populations will be performed, a Bonferroni correction will be applied to correct for multiple comparisons. For the comparison of overall survival and recurrence-free survival between treatment groups, log-rank test will be used. These analysis will be post-protocol analysis based upon data obtained from the standard of care follow up in our post-surgical patients. SAS software will be used for all other statistical analyses.

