## **12.3 Study timetable and end of study**

The end of the study will be defined as the time point 90 days after the final subject receives the infusion of study drug. The recruitment period will take place over a period of 24 months.

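### The survival objectives compare treated patients with historical controls, but the only survival test stated compares the trial arms

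*Combined protocol and SAP*

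**What the plan says.** Section 2.2 sets objective 6 as "Comparison of overall survival in patients treated with either MEDI-4736 alone or MEDI-4736 plus Tremelimumab with historical untreated controls" and objective 7 as "Comparison of recurrence-free survival in patients treated with either MEDI-4736 alone or MEDI-4736 plus Tremelimumab with historical untreated controls". The synopsis objectives and section 8.1.2 repeat both. The synopsis list of secondary endpoints agrees: survival is to be "measured according to our usual routine follow-up protocol and compared with historical controls".

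The analysis plan in section 10.3, and its copy under Statistical Methods in the synopsis, has one sentence on method: "For the comparison of overall survival and recurrence-free survival between treatment groups, log-rank test will be used". It adds that the survival analyses are post-protocol and use routine follow-up data. Section 8.1.2 says of timing that "these data can be evaluated approximately 2 year after surgery".

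**The concern.** The objectives and the test have different comparators. The objectives set treated patients against an external, untreated group. The test sets groups within the trial against each other. An analyst who follows section 10.3 would produce a p-value comparing 8, 8 and 4 patients and report it under an objective about historical controls. An analyst who follows section 2.2 would have to choose the cohort, its eligibility and the starting point of the survival clock with the trial data already in hand. With so few treated patients, those choices could decide the result.

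**Working it through.** **Step 1. What the test compares.** Section 3.1 and the synopsis study design describe comparisons "between treatment groups (MEDI-4736 alone, MEDI-4736+tremelimumab, untreated) following treatment". Section 10.3 itself opens by listing two treatment arms and one untreated arm. Neither place includes a historical group. On the protocol's own usage, the log-rank is between trial arms.

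**Step 2. What is specified for the historical comparison.** The comparator is named in the objectives and the endpoint list. The source, period, eligibility and size of the cohort are not given. Nor are the time origin, a benchmark survival rate, or a sentence tying a test to this comparator.

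**Step 3. Stated figures.** The documents give no power, event count, hazard ratio (HR) or historical rate for survival, so there is no survival figure to reproduce. The one power statement (80%, section 10.1/10.2) concerns the paired t-test on CD8/Treg. It reproduces at 79.7% (n = 8, difference 2.87 − 1.94 = 0.93, SD 0.808, two-sided 5%) and has no bearing here.

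**Step 4. Power of the test as written.** Arm sizes 8, 8 and 4 are from section 10.1/10.2. The HR is an assumption. Every patient is taken to have an event, which is the best case. With E events and a fraction p in one group, power = Φ(|ln HR| × √(E·p·(1−p)) − 1.96).

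- 8 v 8, HR 0.5: 0.693 × √(16 × 0.25) = 1.386; 1.386 − 1.96 = −0.574; power 28%.
- 8 v 4, HR 0.5: 0.693 × √(12 × 2/3 × 1/3) = 1.132; power 20%.
- 16 v 4, HR 0.5: 0.693 × √(20 × 0.8 × 0.2) = 1.240; power 24%.
- 8 v 8 over HR 0.4 to 0.7: power 45% down to 11%. The HR detectable with 80% power is 0.25.

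**Step 5. Power for the stated question.** Assume 100 historical patients and HR 0.5. With d₁ treated and d₀ historical events, power = Φ(0.693/√(1/d₁ + 1/d₀) − 1.96).

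- All patients dead: 8 v 100 gives 0.693/√0.135 = 1.887, power 47%; 16 v 100 gives 0.693/√0.0725 = 2.574, power 73%. With 50 to 200 historical patients these become 44-49% and 68-76%.
- Evaluated about 2 years after surgery, with an assumed 12-month historical median: at HR 0.5 the treated median is 24 months, so 50% of treated patients have events at 2 years. If resections are spread evenly over 24 months and the cut-off is 2 years after the last, this is 1 − (0.50 − 0.25)/0.693 = 64%. Of the historical patients, 75 have events at 2 years, and 100 with long follow-up.
  - 8 treated: d₁ = 4, d₀ = 75 gives 0.693/√0.263 = 1.351, power 27%; d₁ = 5.1, d₀ = 100 gives about 33%.
  - 16 treated: d₁ = 8, d₀ = 75 gives 0.693/√0.138 = 1.864, power 46%; d₁ = 10.2, d₀ = 100 gives about 56%.

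Overall: about 27-47% for 8 treated and 46-73% for 16 pooled, depending on the events observed.

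**Step 6. Why the time origin must be stated.** Section 3.1 allows 3 to 21 days from biopsy to infusion and 7 to 42 days from infusion to resection, so biopsy precedes resection by 10 to 63 days. Suppose resected trial patients were timed from biopsy and historical patients from resection, with an assumed 12-month median and no drug effect. The ratio of medians would be 12/(12 + 10/30.44) = 0.97 to 12/(12 + 63/30.44) = 0.85. Timed from infusion at the longest delay (42 days), it would be 12/(12 + 42/30.44) = 0.90. These figures apply only if the two clocks differ.

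**The case against.** A log-rank test can be run against a patient-level historical group, and the objectives and endpoint list already name the comparator. On that view only a linking sentence and a cohort definition are missing. This stands in part: a reader might infer that the log-rank is the wrong tool, and it is not. What fails is the comparator in section 10.3, which sections 3.1 and 10.3 give as the trial arms.

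A reader might also infer that the follow-up passages contradict each other. Section 12.3 says "The end of the study will be defined as the time point 90 days after the final subject receives the infusion of study drug"; section 7.1.3 gives a minimum of 12 months; section 8.1.2 looks to about 2 years. The documents do not support that reading. The first closes the formal study, the second is a floor followed by routine care that for most patients is lifelong, and the third is a later analysis of routine data. Section 12.3 needs no change.

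It is likewise tempting to say that the plan builds in lead-time bias. No section times survival from biopsy, randomisation or infusion, and the one cue in section 8.1.2 points to surgery. The origin is unstated, not shown to be wrong.

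Finally, this is a pilot study with a CD8/Treg primary endpoint, and survival is labelled post-protocol. That limits the consequence. The label describes when the analysis is done and where its data come from. It does not change which comparison answers an objective still listed as secondary.

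**Conclusion.** The mismatch holds on the text alone and needs no assumption: objectives 6 and 7 name historical untreated controls, and the only survival test stated compares the trial arms. The result would be a p-value that does not answer either objective, with about 28% power (8 v 8, assumed HR 0.5, all patients dead) and less if some are alive.

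Correcting the comparator makes the analysis answer the question; it does not make it well powered. A reader might take 47% and 73% as the power after correction. Those figures require every patient to have died, and an evaluation about 2 years after surgery would give roughly 27-33% and 46-56% on the assumptions in the working. The HR, the 100 historical patients and the 12-month median are all assumptions, since the documents supply none. The point is worth correcting but secondary in importance.

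**What to change.** Replace the survival sentence in section 10.3 and in the synopsis statistical methods so that it provides for the following:

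- Overall and recurrence-free survival in each active arm, and in both pooled, are compared by log-rank, with a hazard ratio and confidence interval, with a named historical cohort resected at the same centre under matching eligibility.
- The time origin is the same in both groups: date of resection, if the historical cohort is defined by resection.
- Treated patients who were never resected are reported separately. Section 4.3 and Appendix B follow them for survival, whereas the evaluable set in section 5.3 is "20 evaluable subjects (if tissue obtained at time of thoracoscopy and time of surgical resection"). A clock started at resection would otherwise drop them unnoticed.
- Between-arm survival curves are labelled descriptive.
- Any power or lead-time figure is given as a range with its assumptions.

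If no suitable patient-level historical cohort exists, restate objectives 6 and 7 as descriptive.

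The cost is wording in two places (plus the objectives, if they are restated) and, for the comparison, one extract of historical patients. Section 1.4 reports 2-4 surgically treated mesothelioma patients per week and section 8.1.2 refers to historical survival estimates, so such a cohort is plausible. The documents do not say that patient-level data are held. No new patients or visits are needed.

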## **11. ETHICAL AND REGULATORY REQUIREMENTS**

### **11.1 Ethical conduct of the study**

The study will be performed in accordance with ethical principles that have their origin in the Declaration of Helsinki and are consistent with ICH/Good Clinical Practice, and applicable regulatory requirements Subject data protection.

### **11.2 Ethics and regulatory review**

MEDI4736 and tremelimumab are both investigational drugs not approved for clinical use in patients with surgically resectable MPM. Our study will undergo review by the Baylor College of Medicine Institutional Review Board. Investigational New Drug applications will also be filed with the FDA.

### **11.3 Informed consent**

Informed consent shall be documented by the use of a written consent form approved by the IRB and the sponsor and signed and dated by the subject or the subject's legally authorized representative at the time of consent. A copy shall be given to the person signing the form.

## **11.4 Changes to the protocol and informed consent form**

Any changes to the protocol or informed consent form will be reviewed by the sponsor and the local IRB prior to implementation. Any changes to the informed consent form that impact currently enrolled subjects (e.g., changes in procedures, changes in the benefit/risk profile) will require that subjects are re-consented with the new consent form.

## **11.5 Audits and inspections**

All records and documents pertaining to the study will be maintained in appropriate permanent files as per the ICH guidelines for Essential Documents for the Conduct of a Clinical Trial and 21 CFR 11, and will be available for inspection by the Sponsor, Sponsor designee, the FDA, or any other designated review body at any time.

# **12. STUDY MANAGEMENT**

The principal investigator assumes all oversight and reporting of the study, including the training of study site personnel and monitoring of the study.

## **12.1 Training of study site personnel**

The PI of this study will train the study coordinator in the procedures necessary to identify and accrue appropriate individuals to the study. The PI of the study will also train the staff scientist in the lab appropriate tissue collection and storage procedures. The co-investigator of this study, [name], will train infusion center staff on appropriate administration of study drugs.

## **12.2 Monitoring of the study**

### **12.2.1 Source data**

Subjects will be monitored closely throughout the course of the study with regular visits with the Study PI and direct access to the PI throughout the duration of the study. The PI is directly responsible for the study subjects, and the study staff will be instructed to contact the PI immediately with any concerns regarding patient safety or other matters.

## **12.3 Study timetable and end of study**

The end of the study will be defined as the time point 90 days after the final subject receives the infusion of study drug. The recruitment period will take place over a period of 24 months.

## **13. DATA MANAGEMENT**

The database that will be utilized for data collection and storage will be OnCORE. The PI and study staff will adhere to the reporting requirements of the data to the institutional IRB.

To ensure the privacy and confidentiality of data for this protocol, the data will be stored on a restricted access location on our institution's server. Access to the project directory containing the data will be limited to the investigators and research staff. Information about data security awareness is promoted through user training and education and supplemented by policies and procedures. Password protection will be used for all transactions that involve viewing, editing, and analyzing the data or that provide access to data fields derived from the original source documents.

The investigator maintains the confidentiality standards of each patient enrolled in the study through the assignment of a unique subject identification number that de-identifies the study information from the patient's health information. The key linking subject code to the patient is kept in an additional secure restricted access location on our institution's server that is only accessible to the study staff. No identifying information, such as the patient's name, will be included in the data sets used for reporting the data. The data released to AstraZeneca will be patient age, histology, and chemotherapy status, as well as CyTOF data, PD-L1 immunohistochemistry data, and nanostring mRNA data. Patient medical information obtained for the study is confidential, and may only be disclosed to third parties as permitted in the Informed Consent Form signed by the subject unless permitted or required by law.

